5.4.4 Parameters to be Monitored

The following progress will be monitored throughout the course of the research to ensure the safety of subjects as well as the integrity and confidentiality of their data.

An evaluation of the progress of the research study, including subject recruitment and retention, and an assessment of the timeliness and quality of the data.

A review of collected data (including adverse events, unanticipated problems, and subject withdrawals) to determine whether there is a change to the anticipated benefit-to-risk assessment of study participation and whether the study should continue as originally designed, should be changed, or should be terminated.

An assessment of external factors or relevant information (eg. pertinent scientific literature reports or therapeutic development, results of related studies) that may have an impact on the safety and study participants or the ethics of the research study.

A review of study procedures designed to protect the privacy of the research subjects and the confidentiality of their research data.

The National Cancer Institute Common Toxicity Criteria Scale will be used to define grades (severity) of adverse events and toxicities. An adverse event is any untoward medical occurrence in a participant who received study drug, regardless of its relationship to the study drug. Toxicity is an adverse event with a direct relationship to the study drug. All toxicities are adverse events, but not all adverse events are toxicities. This is a determination made by the study investigator. The study investigators will classify adverse events as "definitely or most likely," "possibly," or "very unlikely" due to the study drug. Toxicity will be defined as an adverse event that is definitely, most likely, or possibly caused by the study drug.

The severity of adverse changes in physical signs or symptoms will be classified as follows:

Grade 1 (Mild): asymptomatic or mild symptoms; clinical or diagnostic observation only; intervention not indicated.

Grade 2 (Moderate): minimal, local or noninvasive intervention indicated; limiting age-appropriate instrumental ADL (Activities of Daily Living).

Grade 3 (Severe): medically significant but not immediately life-threatening; hospitalization or prolongation of hospitalization indicated; disabling; limiting self care ADL.

Grade 4 (Life-threatening): serious potential consequences; urgent intervention indicated.

Grade 5 (Death): event is a direct cause of death.

5.4.5 Frequency of Monitoring

The principal investigator will review subject safety data as it generated. The principal investigator, co-principle investigators, and the research staff will communicate by conference calls or visits at monthly interval to re-evaluate study goals, subject recruitment, data coding and retention, documentation and identification of adverse events, complaints and confidentiality of subjects. There will be an evaluation of the progress of the research study, including assessments of data quality, time lines, participant recruitment, accrual, and retention. The principal investigator will also review the outcome and adverse event data to determine whether there is any change to the anticipated benefit-to-risk ratio of study participation and whether the study should continue as originally designed or should it be re-evaluated and changed.

5.4.6 Reportable Adverse Events

For this study, a serious adverse event is any untoward clinical event that is thought by the investigator to be study-related, that is also:

- 1. Fatal or immediately life threatening
- 2. Permanently disabling, or severely incapacitating.
- 3. Requires or prolongs inpatient hospitalization.
- 4. Important medical events that may not result in death, be life threatening, or require hospitalization may be considered serious adverse events when, based upon appropriate medical judgment, they may jeopardize the patient, or subject, and may

require medical, or surgical intervention to prevent one of the serious outcomes listed above.

If clinically important and unexpected adverse experiences, or clinically important study-related adverse experiences occur, they will be recorded on the adverse event case report form.

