1.3 BACKGROUND

Idiopathic pulmonary fibrosis (IPF) is a morbid interstitial lung disease that is characterized by lung parenchymal fibroproliferation (1-4). IPF manifests with progressive shortness of breath and hypoxemia. The absence of a valid pathological paradigm has precluded the rational selection of mechanistically-targeted therapy. Only two medications, whose mechanisms of action remain largely speculative (pirfenidone and nintedanib), have been recently shown to have partial efficacy for IPF. IPF continues to have a worse prognosis than many common malignancies, with a median survival of approximately 3 years from the time of diagnosis.

Our recent studies and others (5-21), support an autoimmune pathogenesis, leading us to posit the central hypothesis of this proposal: Antibody-mediated autoimmunity plays an important role in IPF progression. Among these findings, B-cell follicular-like aggregates are evident in IPF lungs (5,6,20), along with over-expressions of immunoglobulin (Ig) genes (8). Antigen-antibody (immune) complexes with considerable pathogenic potential are present in sera, bronchoalveolar lavage (BAL) and lung parenchyma of IPF subjects (7,9,14,20). Injurious complement deposits are also common in IPF lungs (20). Enhanced B-cell differentiation induced by antigen exposure and increased circulating levels of B-lymphocyte stimulating factor (BLyS) are characteristics of autoantibody-mediated diseases, and are similarly increased and proportionate to disease activity among IPF patients (20). Various circulating antibodies with self-avidities are detectible in ~80% of IPF cohorts (10,14). Several of these IPF autoantibodies exert direct cytopathic or other function-altering effects, and/or are associated with clinical manifestations and prognoses of the afflicted individuals (9-17). We have also recently found that CXCL13, an important mediator for B-cell trafficking to inflammatory foci, is similarly increased in lungs and plasma of IPF patients, proportionate to their disease activity, and inversely proportionate to their survival (21).

Other autoantibody-mediated lung diseases are refractory to nonspecific therapies, notably including steroids. In contrast, however, specific treatments to remove or reduce autoantibodies are now a mainstay of therapy for anti-donor HLA antibody-mediated lung transplant rejection and other patients with autoantibody-mediated lung diseases (22-28).

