The PI will work with the reporting investigators to prepare a detailed written summary of serious, unexpected, and treatment related adverse events, and will compare and contrast the event with prior events. The detailed written summary will be provided to the DSMB and the IRB.

In addition, the DSMB Report addressing the following information will be submitted to the IRB at the time of continuing review annually or more often as required:

A list of the research personnel who participated in the data and safety monitoring.

The frequency of monitoring that took place during the renewal intervals and/or the dates that data and safety monitoring was conducted.

A summary of cumulative data related to unanticipated problems (including adverse events) including a determination of causality and whether the risk to benefit assessment has changed.

If appropriate, a summary of pertinent scientific literature reports, therapeutic developments, or results of related studies that may have an impact on the safety of

study participants or the ethics of the research study.

A summary of the outcome of reviews conducted to ensure subject privacy and research data confidentiality.

Final conclusions regarding changes to the anticipated benefit-to-risk assessment of the study participation and final recommendations related to continuing, changing, or terminating the study.

STOPPING RULE:

Individual subject-specific stopping rules:

A study participant will be discontinued from further study drug treatment/Intervention(s) administration if any of the following occur:

Any clinical adverse event, laboratory abnormality, intercurrent illness, other medical condition or situation occurs such that continued participation in the study would not be in the best interest of the participant.

Intercurrent illness or an unexpected fatal or life-threatening adverse event, which requires discontinuation of study treatment

Request by the subject to withdraw from the study

Investigator discretion

A study-wide stopping rule will be based on the comparison of rate of serious adverse events between the two treatment groups. This safety endpoint will be used instead of the primary endpoint since the primary endpoint is not a clinical marker of efficacy, but a biomarker of a clinical outcome. The DSMB and sponsor (NIH) will have responsibility for invoking a study-wide stopping rule based on their evaluations of the data.

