5.4.7 Adverse Events Reporting Timeline

1. Serious and unexpected, suspected adverse reactions to the study drug: The serious and unexpected, suspected adverse reaction will be reported to the DCC and overall study PI as soon as possible, but no later than 15 calendar days after the site Investigator receives the respective information.

All reviewing IRBs will also be notified of serious and unexpected, suspected adverse reactions in accordance with the respective policies and procedures of the IRBs. The DSMB and all Investigators (i.e., study site principal investigators) will also be promptly notified of serious and unexpected, suspected adverse reactions.

2. Unexpected life-threatening or fatal, suspected adverse reactions associated with the use of the study drug: The unexpected, life-threatening or fatal, suspected adverse reaction will be reported to the DCC, overall PI, and DSMB as soon as possible, but no later than 2 working days after the site Investigator receives the respective information.

All reviewing IRBs will also be notified of unexpected, life-threatening or fatal, suspected adverse reactions in accordance with the respective policies and procedures of the IRBs.

All Investigators (i.e., study site principal investigators) will also be promptly notified of these adverse events.

3. Other adverse events (eg, unexpected related adverse events of lesser severity or expected adverse events of any severity): These events will be reported in aggregate form to the DCC, overall study PI, and the DSMB at the time of regular data reports. However, sites will have the option of bringing any event to the immediate attention of the Study PI and DCC (via faxing the interim event report form) for review and discussion by the Steering Committee and for consideration of immediate reporting to the Head of the DSMB. Similarly, the DCC will have the option of bringing any event to the attention of the Steering Committee.

Sites will also follow and comply with their own local institution's adverse event reporting requirements. Depending on the local requirements, a site may report events locally that are not reported to the DCC.

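### The SAE definition requires the investigator to judge the event study-related, so deaths and admissions attributed to IPF drop out of the only named study-wide stopping metric

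*Combined protocol and SAP*

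**What the plan says.** Section 5.4.6 of the combined protocol and SAP sets two conditions for an SAE. The first is attribution: "a serious adverse event is any untoward clinical event that is thought by the investigator to be study-related". The second is that the event also meets one of four seriousness criteria: fatal or life-threatening, disabling, hospitalisation, or medically important.

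The STOPPING RULE text within Section 5.4.3.3 uses that term as its metric: "A study-wide stopping rule will be based on the comparison of rate of serious adverse events between the two treatment groups". It explains that a safety endpoint was chosen because the primary endpoint is a biomarker. It gives no boundary, alpha or schedule of looks, and leaves the decision to judgement: "The DSMB and sponsor (NIH) will have responsibility for invoking a study-wide stopping rule based on their evaluations of the data".

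Elsewhere the document keeps seriousness and causality apart:
- Sections 2.8.2 f and 5.4.4 define an adverse event whatever its relation to treatment. Section 5.4.4 reserves a different word for related events: "All toxicities are adverse events, but not all adverse events are toxicities".
- Section 5.4.3.3 asks for "a detailed written summary of serious, unexpected, and treatment related adverse events", which treats seriousness and relatedness as separate attributes.
- Section 5.4.7 (items 1 and 2) requires that a reaction be suspected, in addition to being serious, life-threatening or fatal.

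**The concern.** IPF often leads to death and hospital admission, so many of the gravest events in either arm may be put down to the disease. Section 5.4.6 removes each of those from the SAE count before the arms are compared. If rituximab raised deaths or admissions through events that resemble disease progression, the SAE rate could stay level while all-cause outcomes diverged. Sections 3.4 and 5.1.2 list infections, dyspnea and bronchospasm among its risks, and these may be hard to tell from IPF worsening.

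Randomisation makes case-by-case attribution unnecessary for this comparison, because background disease events are expected equally in both arms. Filtering on attribution first gives up that advantage and lets differences between investigators affect the safety metric. Section 5.4.6 also does not say which level of the three-level causality scale in Section 5.4.4 makes an event study-related, so sites could count differently.

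**Working it through.** **The definitions side by side.**
1. Section 5.4.6: SAE = judged study-related AND meets a seriousness criterion.
2. Section 5.4.3.3, STOPPING RULE: metric = SAE rate, arm against arm.
3. No other definition of an SAE appears in the document.
4. It follows that a fatal event or admission judged not study-related is not an SAE and is not in the metric. An event attributed partly to IPF but also thought study-related still counts.
5. The threshold in step 1 is undefined. Section 5.4.4 does set one for toxicity ("Toxicity will be defined as an adverse event that is definitely, most likely, or possibly caused by the study drug"), but Section 5.4.6 does not adopt it.

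**The plan's own figures.** None is given for the stopping rule. The one design calculation, 80% power for the primary endpoint in Section 2.9.1, reproduces (81.0% by exact enumeration of the two-sided Fisher test, 33% v 3%, 29 per arm) but has no bearing on this point.

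**How many deaths are at issue (illustration).** Inputs: N = 58 and 9 months of follow-up (Section 2.2), and the disease described in Section 1.3 "with a median survival of approximately 3 years from the time of diagnosis". A constant hazard is assumed, and that median is applied from enrolment.

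9-month mortality = 1 − exp(−9 ln 2 / m), with m the median in months.

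| Median m | 9-month mortality | Expected deaths in 58 |
|---|---|---|
| 36 (Section 1.3) | 15.9% | 9.2 |
| 48 (assumed) | 12.2% | 7.1 |
| 24 (assumed) | 22.9% | 13.3 |

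**How many would be counted.** The documents give no attribution rate. With an assumed fraction f judged study-related, the number counted is 9.2 × f:
- f = 0: 0
- f = 0.25: 2.3
- f = 0.5: 4.6
- f = 1: 9.2

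**What this does not show.** Nine deaths split 7 of 29 v 2 of 29 give a two-sided Fisher p of 0.144. A trial of this size would often not reach significance on deaths even with complete counting.

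**Dilution across all serious events (illustration).** Assume all-cause serious-event rates of 40% v 10%, 29 per arm, a single two-sided Fisher test at 0.05, and the same fraction judged related in both arms. Power is 68% if every event counts, 22% if half do and 3% if a quarter do. For assumed rates of 50% v 20% it is 57%, 20% and 4%. These rates are invented to show the direction and rough size of the loss; they are not estimates for this trial.

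**The case against.** The strongest reply is that the DSMB is not confined to the SAE count.
- It meets at least every six months and reviews adverse event reports and accumulating data (Section 5.4.2).
- Section 5.4.4 calls for review of adverse events, unanticipated problems and withdrawals, with termination as a possible outcome.
- The DSMB Report in Section 5.4.3.3 ends in a recommendation on whether to continue.
- Section 5.4.5 has the principal investigator review outcome and adverse event data.
- Section 5.4.7 item 3, which covers expected events of any severity, states: "These events will be reported in aggregate form to the DCC, overall study PI, and the DSMB at the time of regular data reports".
- The final analysis in Section 2.9.2 compares adverse events and hospitalisations by arm with no causality filter.

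A discretionary rule without a threshold also cannot be shown to fail numerically. The inconsistent usage elsewhere might be read as loose drafting rather than a deliberate restriction, and if possibly related events count, only those judged very unlikely to be related would drop out.

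Much of this stands. It would be wrong to say that the DSMB never sees these events. But none of the interim routes says that all-cause deaths or serious events are shown by arm or linked to the stopping rule. Section 5.4.7 also lets a site report some events locally without sending them to the DCC, and the Section 2.9.2 comparison comes too late for monitoring. The opening words of the definition apply it to this study as a whole, so the literal reading is the stronger one. The inconsistent usage is a further reason to correct the definition.

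**Conclusion.** The concern holds, and the definition is wrong as written. Under Sections 5.4.6 and 5.4.3.3 read together, deaths and admissions attributed to IPF do not enter the one metric named for stopping the study, and detecting an imbalance in them depends on the DSMB looking beyond that metric.

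This conclusion rests on the text alone. Its size can only be illustrated. About 9 deaths are expected at a 3-year median (7 to 13 for medians of 4 to 2 years), under a constant hazard and with a median measured from diagnosis. Between none and all of them would be counted, because no attribution rate is given. No effect on the rule's error rates can be calculated, and there is no claim that a significant difference would be missed. The defect lies in which events the DSMB is directed to compare.

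**What to change.** **Essential changes**
- Section 5.4.6: remove the relatedness condition, so that the four seriousness criteria alone define an SAE.
- Record causality as a separate field on the Section 5.4.4 scale, and use it for expedited reporting.
- Section 5.4.3.3, STOPPING RULE: state that the comparison between arms uses all-causality SAEs and all-cause deaths.

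**Minor clarifications**
- Section 5.4.6: say that its closing sentence on the case report form does not narrow the Section 5.4.3.3 requirement to record all untoward occurrences, and that this requirement covers both arms.
- Sections 5.4.3.1 and 5.4.3.3: say whether routine SAE reports to local IRBs and the Coordinating Center cover all SAEs or only related ones.

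**Cost.** Protocol wording and a case report form instruction, more SAE forms, and more routine SAE reports unless those are limited to related events. The expedited triggers in Sections 5.4.7 and 5.4.8 do not change, since they depend on suspected reactions or unanticipated problems. Forwarding oversight-body correspondence to NHLBI under the end of Section 5.4.8 could grow somewhat. Survival and hospitalisations are already tabulated under Section 2.8.2, so those two components need no new data collection.

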- **e.) Hospitalizations** Indirect evidence of treatment efficacy could also be discerned by reductions of subsequent needs for hospital admissions. The frequencies and durations of hospitalizations among trial subjects will be tabulated and analyzed.
- **f.) AE Monitoring-** The National Cancer Institute Common Toxicity Criteria Scale will be used to define grades (severity) of AE and toxicities. An AE is defined as any untoward medical occurrence in a subject, regardless of its relationship to these treatments. Toxicity is an AE with a direct relationship to the study drug. All toxicities are AE, but not all AE are toxicities.

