Linear regression models will be used to assess the treatment effect on continuous variable secondary endpoints. Main effects will include treatment, the stratification variables, and unbalanced baseline characteristics. Both the proportion of individuals with AEs and the count of AEs per person will be compared by treatment. A logistic regression model will be used to compare the proportion of subjects with acute exacerbations, hospitalizations, or adverse events (AEs) by treatment group, with main effects as described above. A negative binomial model will be used to evaluate the average count of AEs per subject by treatment group. For all models, the model assumptions (e.g., normality of residuals, over dispersion) will be investigated. If the assumptions are violated, transformations will be investigated. If adequate transformations cannot be identified, nonparametric approaches will be utilized. Small cell sizes may exist and exact methods may need to be employed.

Additional exploratory analyses will be conducted. This may include the use of mixed-effects regression models to examine the longitudinal course of the outcomes as well as survival analyses (e.g., Kaplan-Meier curves, log-rank test, Cox proportional hazards models) to evaluate time to event outcomes, such as time to death.

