The mechanisms responsible for beneficial clinical effects of rituximab are complex and incompletely understood, but include elimination of autoantigen-reactive CD20⁺ memory cells (plasma cell precursors), as well as alterations of B-cell antigen presentation, or B-cell costimulatory and/or chemotactic functions. Rituximab obviates or reduces deleterious effects of pathogenic autoantibodies. It has been used in thousands of patients over many years, and has a well-characterized and acceptable safety profile, unlike other much more experimental anti-B-cell agents (e.g., alemtuzumab, bortezomib, etc.). These other treatments are less specific, more toxic, and have only rarely been used in autoimmune patients. Their safety and efficacy for therapy of autoantibody diseases are unknown.

Reported serious adverse events (AE) following rituximab treatment include fatal transfusion reactions, although these seem to occur primarily in lymphoma patients and may be indistinguishable or overlap with tumor lysis syndrome (29-39,42) Serious transfusion reactions to rituximab have occurred in <1% of RA patients. Reactions occurring in >5% of these subjects were nausea (8%), hypertension (8%), upper respiratory tract infections (7%), and arthralgia (6%). Corresponding event rates in placebo controls were: 5%,5%,6%, and 4%, respectively. Uncommon or rare events include mucocutaneous reactions, progressive multifocal leukoencephalopathy, hepatitis B reactivations, and rare infections (29-39,42).

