5.4.3.3 Participating Institutions

Each Participating Institution will provide to the Coordinating Center a list of the key personnel assigned to the role for oversight of data management at their site. The general responsibilities for each Participating Institution are as follows:

Commit to accrual to the multi-center protocol.

Submit protocol and/or amendments to their local IRB.

Maintain a regulatory binder.

Update Coordinating Center with research staff changes on a timely basis.

Submit source documents, research records, and CRFs per protocol specific submission guidelines to the Coordinating Center.

Submit Serious Adverse Event reports to local IRB and provide copies to the Coordinating Center

Submit deviations and violations to local IRB and the Coordinating Center.

Assuring patient safety is an essential component of this protocol. The study Principal Investigator has primary responsibility for the oversight of the data and safety monitoring. The study investigators will evaluate all adverse events. All subjects who have AEs, whether considered associated with the use of the study medication or not, must be monitored to determine the outcome. The clinical course of the AE will be followed up according to accepted standards of medical practice, even after the end of the period of observation, until a satisfactory explanation is found or the Principal Investigator considers it medically justifiable to terminate follow-up.

All untoward medical occurrences observed in subjects receiving the study drug will be recorded on the participants' adverse event case report forms (CRF) by the study coordinator under the supervision of the principal investigator. The CRFs will then be reviewed for completeness and internal consistency. Subsequently, the CRFs will be recorded on an electronic password-guarded study database. In addition to internal safeguards built into a computerized system, external safeguards will be put in place to ensure that access to the computerized system and to the data is restricted to authorized personnel. Training conducted by qualified individuals on a continuing basis will be provided to individuals in the specific operations with regard to computerized systems that they are to perform during the course of the study.

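### Sections 5.4.6 and 5.4.3.3 give different rules for what goes on the adverse event form, and the narrower rule does not match the AE-rate endpoint

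*Combined protocol and SAP*

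**What the plan says.** Two sections say what is entered on the adverse event case report form (CRF).

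- Section 5.4.3.3, Participating Institutions: "All untoward medical occurrences observed in subjects receiving the study drug will be recorded on the participants' adverse event case report forms".
- Section 5.4.6, Reportable Adverse Events, last sentence: if "clinically important and unexpected adverse experiences, or clinically important study-related adverse experiences occur, they will be recorded on the adverse event case report form".

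The endpoint is defined broadly. Section 2.8.2(f) states: "An AE is defined as any untoward medical occurrence in a subject, regardless of its relationship to these treatments". Section 5.4.4 agrees: "An adverse event is any untoward medical occurrence in a participant who received study drug, regardless of its relationship to the study drug". Its severity scale starts at grade 1, which includes events without symptoms. Section 2.9.2 gives the analysis: "Both the proportion of individuals with AEs and the count of AEs per person will be compared by treatment".

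Section 5.4.7 item 3 sends the remaining events, including expected ones of any severity, in aggregate to the DCC, the overall study PI and the DSMB. The section closes by noting that, depending on local requirements, "a site may report events locally that are not reported to the DCC".

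**The concern.** The form that supplies the AE endpoint has two entry rules. One matches the endpoint definition. The other adds a judgement of clinical importance and then a judgement of expectedness or causality, although the endpoint definition sets causality aside. The protocol does not say which rule governs.

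AE rate is a named secondary endpoint, analysed per subject as a proportion and as a count. If some of the five sites enter everything and others apply the 5.4.6 test, site differences in AE counts will partly reflect the recording rule. Minor events are the most exposed. Section 2.10.2 expects no significant excess of high-grade events on rituximab, so lower-grade events may carry much of what this endpoint can show.

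**Working it through.** The plan gives no expected AE rate, event count or power for the AE endpoint, so there is no stated figure to reproduce. The check is mainly textual.

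**Step 1. The rules side by side.**

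| Section | Governs | Events covered |
|---|---|---|
| 2.8.2(f) | Endpoint definition | All, whatever the relationship |
| 5.4.4 | Definition and grading | All, whatever the relationship, from grade 1 |
| 5.4.3.3 | Entry on the AE form | All |
| 5.4.6, last sentence | Entry on the AE form | Clinically important AND (unexpected OR study-related) |
| 5.4.7 item 3 | Aggregate reporting | Includes expected events of any severity |

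**Step 2. What lies between the two form rules.** The events in 5.4.3.3 that 5.4.6 does not name are:

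- events judged not clinically important, whatever their cause; and
- clinically important events that are both expected and judged unrelated.

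Clinically important events judged study-related are named in 5.4.6 even when expected.

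**Step 3. What the analysis needs.** The proportion with an AE and the count per person both need subject-level records. Section 6.7.2 makes CRFs the main data collection instrument, and 5.4.3.3 describes the AE form feeding the study database. No other subject-level AE source is described. Aggregate totals under 5.4.7 cannot give either quantity. Section 6.7.2 also plans no imputation for safety data, so an event left off the form is not restored later.

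**Step 4. Illustration of direction, not an estimate of loss.** Section 3.4 gives rates in rheumatoid arthritis (RA) patients for nausea, hypertension, upper respiratory infection and arthralgia of 8%, 8%, 7% and 6% on rituximab. "Corresponding event rates in placebo controls were: 5%,5%,6%, and 4%, respectively".

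- Rituximab: 8 + 8 + 7 + 6 = 29 per 100. Placebo: 5 + 5 + 6 + 4 = 20 per 100. Ratio 29/20 = 1.45.
- At 29 per arm, assuming RA rates carry over: 29 × 0.29 = 8.41 v 29 × 0.20 = 5.80, difference 2.61.

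Let *c* be the share of these events that is recorded. The documents give no value, so the shares below are assumptions. With equal *c* in both arms:

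| c | Rituximab | Placebo | Difference | Ratio | SE of log ratio, multiplied by 1/√c |
|---|---|---|---|---|---|
| 1.00 | 8.41 | 5.80 | 2.61 | 1.45 | 1.00 |
| 0.75 | 6.31 | 4.35 | 1.96 | 1.45 | 1.15 |
| 0.50 | 4.21 | 2.90 | 1.31 | 1.45 | 1.41 |
| 0.25 | 2.10 | 1.45 | 0.65 | 1.45 | 2.00 |

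The last column treats counts as Poisson. With overdispersion, as the planned negative binomial model allows, the inflation is smaller.

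With unequal capture the recorded ratio is 1.45 × c(rituximab)/c(placebo). Capture of 0.50 v 0.75 gives 1.45 × 0.667 = 0.97; capture of 0.75 v 0.50 gives 1.45 × 1.5 = 2.18. The bias can go either way. Blinding limits this but need not remove it: if the kinds of event differ by arm, and investigators call some kinds related more readily than others, capture can differ by arm without anyone knowing the assignment.

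**The case against.** The strongest reply is that the two sections can be obeyed together. Section 5.4.6 says certain events will be recorded; it does not say that others will not. It stands beside the serious-event definition under a heading about reporting, so a site that enters everything under 5.4.3.3 breaches nothing. There are controls too: the DCC trains all clinical personnel (2.9.3, 5.4.3.2), forms have a common format (6.2.1), sites are visited and audited (6.6), monthly calls cover AE documentation (5.4.5), and Appendix A marks AE assessment at all 15 contacts.

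Much of this stands, and it rules out several stronger readings that a reader might infer:

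- *That the form is restricted to the 5.4.6 events.* The restrictive word is absent.
- *That common rituximab effects will be missed.* Important related effects are captured even when expected, and nothing is lost where 5.4.3.3 is followed. Section 3.4 gives no grades for the four reactions, so it does not show that the excess is low-grade. Treating the risks listed in 5.1.2 as the expected events is also an assumption, because the protocol does not define expectedness that way.
- *That the DSMB will not see expected events.* Section 5.4.7 item 3 routes them there in aggregate, and section 5.4.2 does not say that DSMB reports come from this form alone.
- *That the arm difference is understated by about 2.6 events.* That needs zero capture and RA rates, neither supported. Equal capture leaves the ratio at 1.45.
- *That the last sentence of 5.4.7 lets sites withhold AEs.* It accommodates local reporting rules and does not cancel 5.4.3.3.

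What the reply does not answer is why 5.4.6 states a recording condition at all if everything is already recorded. Training, calls and audits enforce whichever rule the sites are given; they do not settle which one it is.

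**Conclusion.** The conflict is real and should be resolved. Sections 5.4.3.3 and 5.4.6 set different entry rules for one form, and the 5.4.6 rule is narrower than the definition on which the AE-rate endpoint rests. Under-recording of minor events, and of events both expected and unrelated, is possible; the documents do not make it certain.

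If it occurs, absolute counts and precision fall, and counts come to depend on site and on investigator judgement. The arm comparison on the ratio scale is biased only if capture differs by arm, and the direction cannot be predicted. The documents give no capture share, so no size can be put on the loss; the table above illustrates direction under assumed shares and borrowed RA rates. This is a wording defect affecting a secondary endpoint. It does not touch the primary analysis.

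**What to change.** Replace the last sentence of 5.4.6 with the 5.4.3.3 rule: every untoward event in either arm is entered on the AE CRF. State that importance, expectedness and relationship decide how quickly an event is reported, not whether it is recorded. Name both arms explicitly, since 5.4.3.3 and 5.4.4 speak of those given study drug while 2.8.2(f) speaks of any subject.

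Clarify the last sentence of 5.4.7 so that differing local reporting requirements do not exempt any AE from entry on the AE CRF and in the study database.

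The cost is a protocol wording change, site retraining and some additional low-grade entries. No new visits are needed, because AE assessment is already scheduled at every contact in Appendix A.
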